5.5.3 Labelling

Labels will be prepared in accordance with Good Manufacturing Practice (GMP) and local regulatory guidelines. The labels will fulfil GMP Annex 13 requirements for labelling. Label text will be translated into the local language.

5.5.4 Storage

All IP should be kept in a secure place under appropriate storage conditions. The IP label on the bottle will specify the appropriate storage.

5.6 Concomitant and post-study treatment(s)

Study screening will begin up to 60 days prior to the baseline visit to allow a washout period for patients taking oral contraceptives. Patients who discontinue oral contraceptives must demonstrate acceptable LH and testosterone levels upon repeat assessments on Days -21 to -2 prior to the baseline visit (see Section 4.1 and Section 4.2 for inclusion and exclusion criteria, respectively).

Concomitant use of AZD4901 with narrow therapeutic index drugs that are metabolised by *CYP3A4/5* should be avoided. The coadministration of potent and moderate inhibitors and inducers of *CYP3A4* and *CYP2C9* is prohibited for the time frames described in Table 3. Given the potential for AZD4901 to interact with *CYP3A4*, the suitability of coadministration of drugs metabolised by *CYP3A4* should be guided by the approved label for that drug and recommendation for coadministration with *CYP3A4* inhibitors and inducers.

The use of concomitant medications that prolong the QT/QTc interval is prohibited.

The use of oral, transdermal, or implantable hormonal contraception and oestrogen, progesterone or androgens; and antiandrogenic drugs, 5- α -reductase inhibitors, GnRH analogs, ovulation induction drugs, and anti-progestogens are restricted for time frames provided in Table 3. Antidiabetic medications, including metformin used to treat PCOS symptoms, should be stable for the time frame specified in Table 3.

Table 3 Restricted medications

Therapy	Time frame
Potent and moderate CYP3A4 inhibitors, including but not limited to: cyclosporine, systemic (oral/intravenous) itraconazole, ketoconazole, fluconazole, erythromycin, clarithromycin, telithromycin, nefazodone, HIV protease inhibitors, aprepitant, verapamil, and diltiazem	4 weeks prior to screening and throughout the study period

Table 3 **Restricted medications**

Therapy	Time frame
Potent and moderate CYP3A4 inducers, including but not limited to: rifampicin, rifabutin, carbamazepine, phenytoin, barbiturates, systemic glucocorticoids (replacements and inhaled are permitted), nevirapine, efavirenz, pioglitazone, primidone, and St. John's wort	4 weeks prior to screening and throughout the study period
Potent and moderate CYP2C9 inhibitors, including but not limited to: amiodarone, fluconazole, miconazole, and oxandralone	4 weeks prior to screening and throughout the study period
Potent and moderate CYP2C9 inducers, including but not limited to: carbamazepine and rifampin	4 weeks prior to screening and throughout the study period
Antidiabetic medications, including metformin administered for PCOS	Stable dose for 8 weeks prior to screening and throughout the study period
Oral contraception, transdermal or implantable hormonal contraception, oestrogen, progesterone, or androgens	8 weeks prior to dosing and throughout the study period
Antiandrogenic drugs (eg, spironolactone, any other antiandrogenic drugs), 5- α -reductase inhibitors, GnRH analogs (eg, Lupron [®] , any others), ovulation induction drugs (eg, clomiphene and any other antiestrogenic compounds, and gonadotropins, including all forms of FSH, LH, and human chorionic gonadotropin), and anti-progestogens	12 weeks prior to screening and throughout the study period

If any medication is necessary, it should be prescribed by the Investigator, and the AstraZeneca Clinical Pharmacology Alliance (CPA) Physician should be informed. Information on any treatment in the 12 weeks prior to starting study treatment and all concomitant treatments given during the study, with reasons for the treatment, will be recorded in the case report form (CRF).

5.7 Treatment compliance

The administration of all study drugs (including IP) should be recorded in the appropriate sections of the CRF.

Patients will be given a diary card at the Day -1 (baseline) visit for recording of the dates and times of all IP administration. The diary cards will be reviewed at each clinic visit for treatment compliance. On Days 6 and 27 (the days prior to serial PK sample collection), the site will contact patients by telephone to confirm recording of the dates and times of dosing

has been completed and to remind patients to hold the morning doses on Days 7 and 28 until clinic arrival.

Accountability

The IP provided for this study will be used only as directed in this CSP. The study personnel will account for all IP dispensed to and returned from the patient.

Study site personnel will account for all IP received at the site, unused IP, and for appropriate destruction or return (as applicable). Certificates of delivery, destruction, and return (as applicable) should be signed.

5.8 Discontinuation of investigational product

Patients will be discontinued from IP in the following situations:

- Patient decision. The patient is at any time free to discontinue treatment, without prejudice to further treatment
- The patient has a clinically significant or serious AE that would not be consistent with continuation in the study, as determined by the Investigator, AstraZeneca or representative, or the patient
- Patient has a positive pregnancy test
- Severe noncompliance to study protocol
- A patient reporting suicidal ideation of Type 4 or 5 or suicidal behaviour as measured by the C-SSRS during the study will be discontinued and referred for appropriate assessment and treatment.

If a patient discontinues from the study prematurely, every effort should be made to conduct a discontinuation visit (see Section 6.2.2).

Patients will discontinue treatment with AZD4901 if any of the following are observed:

- Increase in ALT or AST to a level higher than 5 times ULN, or
- Increase in ALT or AST more than 3 times ULN and signs and symptoms of possible hepatic injury (fatigue, nausea, vomiting, or right upper quadrant tenderness) or drug allergy (fever, rash, or eosinophilia), or
- Increase in ALT or AST more than 3 times ULN and total bilirubin >2 times ULN

If an increase in ALT or AST more than 3 times ULN but less than 5 times ULN with normal total bilirubin level and no signs or symptoms of possible hepatic injury occurs, this will be confirmed with a repeat test immediately. If the repeat ALT and AST are trending up, the

patient must be discontinued from the study. However, if the repeat ALT and AST levels are trending down, the elevations may be monitored for up to 14 days from the initial finding with a frequency of 2 to 3 times per week. If the levels have not normalised by the fourteenth day after the initial finding, the patient must be discontinued from the study.

In case a patient shows an AST or ALT 3 or more times ULN and total bilirubin 2 or more times ULN, please refer to [Appendix D](#) ‘Actions Required in Cases of Combined Increase of Aminotransferase and Total Bilirubin – Hy’s Law’ for further instructions.

Procedures for discontinuation of a subject from investigational product

A patient who decides to discontinue IP will always be asked about the reason(s) and the presence of any AEs. If possible, they will be seen and assessed by an Investigator(s). Adverse events will be followed up (see Section 6.3.3 and Section 6.3.4); dosing diary cards, symptoms diary questionnaires, and all IP should be returned by the patient.

If a patient is withdrawn from study, see Section 5.9.

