14. Positive human immunodeficiency virus (HIV), hepatitis B, or hepatitis C serology evaluations at the screening visit
15. Patient has a history of hypersensitivity to more than 2 chemical classes of drugs, including prescription and over-the-counter medications

16. Past (within 1 year of enrolment) or present alcohol or substance abuse or a positive test for alcohol or drugs of abuse at screening or is a “recreational user” of illicit drugs or prescription medications
17. Patient consumes 3 or more alcoholic drinks per day (Note: 1 drink = 12 oz [360 mL] can/bottle of beer, 4 oz [120 mL] of wine, or 1 oz [30 mL] of liquor)
18. Has received another new chemical entity (defined as a compound which has not been approved for marketing) or has participated in any other clinical study that included drug treatment within at least 3 months of the first administration of IP in this study. The period of exclusion begins 3 months after the final dose or 1 month after the last visit, whichever is the longest. (Note: patients consented and screened, but not randomised in this study or a previous study are not excluded.)
19. Blood loss in excess of 200 mL within 30 days of Day -1, in excess of 500 mL within 56 days of Day -1, in excess of 1350 mL within 1 year of Day -1, or donation of blood products within 14 days of Day -1
20. Patient has a history of neoplastic disease within 5 years prior to signing informed consent, except for adequately treated basal cell, squamous cell skin cancer, or in situ cervical cancer
21. Involvement in the planning and/or conduct of the study (applies to any AstraZeneca employee and their close relatives and/or staff at the study site, regardless of their role in accordance with their internal procedures) or
22. Previous randomisation to treatment in the present study
23. Inability to understand or cooperate with the requirements of the study
24. Patient is legally or mentally incapacitated
25. Patient has abnormal screening laboratory values as per the guidelines listed below or other clinically significant, unexplained laboratory abnormality according to the Investigator:
 - Aspartate aminotransferase (AST) >1.5 times ULN
 - Alanine aminotransferase (ALT) > 1.5 times ULN
 - Total bilirubin >1.5 times ULN
 - Serum creatinine >2.0 times ULN
 - Hematocrit less than the lower limit of normal
 - Prolactin >2.0 times the ULN

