2. DEFINITIONS

Potential Hy's Law (PHL)

Aspartate Aminotransferase (AST) or Alanine Aminotransferase (ALT) $\geq 3x$ Upper Limit of Normal (ULN) **and** Total Bilirubin (TBL) $\geq 2xULN$ at any point during the study irrespective of an increase in Alkaline Phosphatase (ALP). The elevations do not have to occur at the same time or within a specified time frame.

Hy's Law (HL)

AST or ALT $\geq 3x$ ULN **and** TBL $\geq 2xULN$, where no other reason, other than the IMP, can be found to explain the combination of increases, eg, elevated ALP indicating cholestasis, viral hepatitis, another drug. The elevations do not have to occur at the same time or within a specified time frame.

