4. FOLLOW-UP

4.1 Potential Hy's Law Criteria not met

If the patient does not meet PHL criteria the Investigator will:

- Inform the AstraZeneca representative that the patient has not met PHL criteria.
- Perform follow-up on subsequent laboratory results according to the guidance provided in the Clinical Study Protocol.

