4.2 Potential Hy's Law Criteria met

If the patient does meet PHL criteria the Investigator will:

- Notify the AstraZeneca representative who will then inform the central Study Team

The Study Physician contacts the Investigator, to provide guidance, discuss and agree an approach for the study patients' follow-up and the continuous review of data. Subsequent to this contact the Investigator will:

- Monitor the patient until liver biochemistry parameters and appropriate clinical symptoms and signs return to normal or baseline levels, or as long as medically indicated
- Investigate the etiology of the event and perform diagnostic investigations as discussed with the Study Physician
- Complete the three Liver CRF Modules as information becomes available
- If at any time (in consultation with the Study Physician) the PHL case meets serious criteria, report it as an SAE using standard reporting procedures

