5. REVIEW AND ASSESSMENT OF POTENTIAL HY'S LAW CASES

The instructions in this Section should be followed for all cases where PHL criteria were met.

No later than 3 weeks after the biochemistry abnormality was initially detected, the Study Physician contacts the Investigator in order to review available data and agree on whether there is an alternative explanation for meeting PHL criteria other than DILI caused by the IMP. The AstraZeneca Medical Science Director and Global Safety Physician will also be involved in this review together with other subject matter experts as appropriate.

According to the outcome of the review and assessment, the Investigator will follow the instructions below.

If there **is** an agreed alternative explanation for the ALT or AST and TBL elevations, a determination of whether the alternative explanation is an AE will be made and subsequently whether the AE meets the criteria for a SAE:

- If the alternative explanation is **not** an AE, record the alternative explanation on the appropriate CRF
- If the alternative explanation is an AE/SAE, record the AE /SAE in the CRF accordingly and follow the AZ standard processes

If it is agreed that there is **no** explanation that would explain the ALT or AST and TBL elevations other than the IMP:

- Report an SAE (report term 'Hy's Law') according to AstraZeneca standard processes.

- The ‘Medically Important’ serious criterion should be used if no other serious criteria apply
- As there is no alternative explanation for the HL case, a causality assessment of ‘related’ should be assigned.

If, there is an unavoidable delay, of over 3 weeks, in obtaining the information necessary to assess whether or not the case meets the criteria for HL, then it is assumed that there is no alternative explanation until such time as an informed decision can be made:

- Report an SAE (report term ‘Potential Hy’s Law’) applying serious criteria and causality assessment as per above
- Continue follow-up and review according to agreed plan. Once the necessary supplementary information is obtained, repeat the review and assessment to determine whether HL criteria are met. Update the SAE report according to the outcome of the review

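### Section 5.8 has no liver rule for asymptomatic ALT/AST above 3 and up to 5 times ULN when bilirubin is above normal but not above 2 times ULN

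*Protocol*

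**What the plan says.** Section 5.8 of the protocol has three liver stopping bullets: ALT or AST above 5 times ULN; ALT or AST above 3 times ULN with clinical evidence of hepatic injury or drug allergy; and "Increase in ALT or AST more than 3 times ULN and total bilirubin >2 times ULN". The third says nothing about whether the two rises must coincide.

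A separate paragraph sets a repeat-test rule. It begins "If an increase in ALT or AST more than 3 times ULN but less than 5 times ULN with normal total bilirubin level" and also requires that there be no clinical evidence of hepatic injury. The test is repeated immediately. The patient stops if values are rising. If they are falling, she is monitored two to three times a week for up to 14 days and stops if they have not normalised by then.

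Section 5.8 ends by referring cases to Appendix D with inclusive limits: "In case a patient shows an AST or ALT 3 or more times ULN and total bilirubin 2 or more times ULN". Appendix D Section 2 defines potential Hy's Law (PHL) with the same inclusive limits at any point in the study and adds: "The elevations do not have to occur at the same time or within a specified time frame".

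Appendix D 4.1, for cases that do not meet PHL, says: "Perform follow-up on subsequent laboratory results according to the guidance provided in the Clinical Study Protocol". Appendix D 4.2, for cases that do, lists notification, an agreed follow-up approach, investigation, CRF modules and SAE reporting, and includes "Monitor the patient until liver biochemistry parameters and appropriate clinical symptoms and signs return to normal or baseline levels". Neither these sections nor Appendix D Section 5 says whether to hold or stop investigational product (IP).

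**The concern.** The repeat-test rule ends where bilirubin leaves the normal range, and the combined stop begins only above 2 times ULN. Nothing in Section 5.8 covers the band between them for a patient without symptoms. Appendix D does not close it: cases short of PHL go back to a protocol that has no rule for them, and for PHL cases it gives no dosing instruction.

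This matters because Section 1.4 names a nonclinical potential for hepatotoxicity and relies on liver monitoring as the safeguard. Investigators at several sites would have to decide on continued dosing without a fixed rule, in the pattern where ALT/AST and bilirubin are both raised. The study-level stopping criterion in Section 5.8.1 also counts events that meet individual stopping criteria, so the Section 5.8 limits feed into it. The primary endpoint, sample size and analysis are not affected.

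**Working it through.** There is no figure to reproduce. The check applies the rules as written to pairs of values.

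Inputs, with A = ALT or AST and B = total bilirubin, both in multiples of ULN:
- Stop if A > 5, or A > 3 with listed signs or symptoms, or A > 3 and B > 2 (Section 5.8 bullets).
- Repeat test if 3 < A < 5, B normal, and no signs of hepatic injury (Section 5.8 paragraph). I take normal to mean B ≤ 1.
- PHL if A ≥ 3 and B ≥ 2 (Appendix D Section 2).

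Results for a patient without signs or symptoms. The last column uses the wording proposed under the fix and assumes no earlier qualifying rise:

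| A | B | Section 5.8 as written | PHL? | Proposed wording |
|---|---|---|---|---|
| 4.0 | 0.9 | repeat test | no | repeat test |
| 4.0 | 1.2, 1.5, 1.9 | no liver rule | no | repeat test |
| 4.0 | 2.0 | no liver rule | yes | stop |
| 4.0 | 2.5 | stop | yes | stop |
| 3.0 | 1.0 | no liver rule | no | repeat test |
| 3.0 | 2.0, 2.5 | no liver rule | yes | stop |
| 5.0 | 1.0 | no liver rule | no | repeat test |
| 5.0 | 2.0 | no liver rule | yes | stop |
| 5.1 | any | stop | if B ≥ 2 | stop |

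**Main gap.** At A = 4.0, moving from B = 0.9 to B = 1.2 removes the mandatory retest, and no Section 5.8 liver rule applies again until B exceeds 2.0.

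**Boundary PHL cases.** Two sets meet PHL without a mandatory stop: A exactly 3.0 with B of 2 or more (with or without symptoms, since the symptom bullet is also strict), and asymptomatic A above 3 up to 5 with B exactly 2.0. The repeat test misses them because B is not normal.

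**Timing.** Take A = 4, B = 1 at one visit and A = 1, B = 2.5 at a later one. This is PHL under Appendix D. If the stopping bullet is read as requiring both rises together, the first visit leads only to the repeat test and the second triggers nothing in Section 5.8. If the bullet is read as covering any time, it stops the patient.

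**Entry.** Criterion 25 in Section 4.2 excludes "Total bilirubin >1.5 times ULN". A patient with B between 1 and 1.5 can therefore pass that limit and start outside the repeat-test rule, although other criteria make this less likely.

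**Review deadline.** Appendix D Section 5 says: "No later than 3 weeks after the biochemistry abnormality was initially detected, the Study Physician contacts the Investigator". Counted from detection on Day 7, 14, 21 or 28, that is 7 + 21 = Day 28, 14 + 21 = Day 35, 21 + 21 = Day 42 or 28 + 21 = Day 49. On nominal days the limit never falls before the last dose on Day 28. The earlier contact in Appendix D 4.2 has no stated deadline.

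**Overlap.** The symptom bullet includes drug-allergy signs, but the repeat-test rule excludes only signs of hepatic injury. A = 4 with rash and normal bilirubin therefore meets both rules. A repeat value that is unchanged, neither rising nor falling, is not assigned to either outcome.

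The sections of Amendment 4 shown do not alter Section 5.8.

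**The case against.** The strongest reply is that the limits serve different purposes. Section 5.8 sets a mandatory stop, while Appendix D sets a wider net for identification, review and reporting. An inclusive review threshold beside a strict stopping threshold can be a graded scheme. That is fair, and the difference between strict and inclusive limits should not by itself be called a contradiction. It does not answer the main gap, which lies between two rules of Section 5.8 itself.

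Second, these patients are not unmanaged. Section 6.3.5 requires repeat testing of out-of-range values suspected to be clinically significant and refers to Appendix D on either abnormality alone. Appendix D Section 3 provides an immediate laboratory alert and prompt review. Appendix D 4.2 brings in the Study Physician, and Section 5.8 allows a stop for a clinically significant or serious AE. All of this stands, so a reader who inferred that such patients have no oversight would be wrong. What is absent is a dosing rule. The AE route is a weak substitute for an asymptomatic rise, because Section 6.3.3 makes a worsened protocol laboratory value an AE only if it is serious or is the reason for stopping.

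Third, exact-boundary values are rare, and the non-concurrent gap exists only on one reading. Both points are right, which is why they are secondary here.

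Fourth, entry is tighter than the bilirubin limit suggests. Section 4.2 also excludes Gilbert's syndrome, significant hepatic disease and other clinically significant unexplained laboratory abnormalities. This makes a raised starting bilirubin less likely but does not rule it out.

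Finally, the three-week limit is an outer bound for judging cause, not a dosing deadline, and results from Day 28 follow the last dose anyway. The limit shows only that the Appendix D review cannot be relied on to fill the gap.

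**Conclusion.** The concern holds as a badly fixed safety rule that should be corrected. Followed literally, Section 5.8 requires action on isolated ALT/AST of 4 times ULN but none under its liver rules when bilirubin is also raised, up to and including 2 times ULN. The boundary and timing points add to this but would not carry it alone.

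Few patients are expected. The documents give no rate of ALT, AST or bilirubin rises, so no frequency is claimed. The conclusion rests on reading normal bilirubin as not above ULN and on taking the inequalities as written. A reader might infer that the protocol lets patients with Hy's Law patterns continue in general. The documents do not support that: above 3 and 2 times ULN together, the stop is mandatory, and oversight exists throughout.

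**What to change.** 1. In the Section 5.8 repeat-test paragraph, set the condition to: *ALT or AST ≥3 to ≤5 times ULN, total bilirubin <2 times ULN, PHL criteria not met, and no signs or symptoms of hepatic injury or drug allergy*. State that an unchanged repeat counts as not trending down and leads to discontinuation.
2. Replace the combined stopping bullet with *meets PHL criteria (Appendix D Section 2)*, which also settles timing, and use ≥3 times ULN in the symptom bullet.
3. Add to Appendix D 4.2: *Stop IP as required by Section 5.8.*

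Every ALT or AST of 3 times ULN or more then leads either to a stop or to the repeat test, and not to both.

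The cost is wording, with no added scheduled visits. A rare patient stops early and loses Day 28 data; one stopped on Day 7 results still has the Day 7 LH profile. A few more patients enter repeat testing: two to three draws a week over 14 days is 4 to 6 draws, or 8 to 12 mL at the 2.0 mL clinical chemistry volume in Table 5, plus the immediate repeat. Section 7.1 leaves 530 − 520.5 = 9.5 mL under its cap, so these draws can exceed it, as the existing rule already can. The protocol should say that safety repeats fall outside the cap.

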For SAEs, causal relationship will also be assessed for other medication and study procedures. Note that for SAEs that could be associated with any study procedure the causal relationship is implied as ‘yes’.

A guide to the interpretation of the causality question is found in [Appendix B](#) to this CSP.

Adverse Events based on signs and symptoms

All AEs spontaneously reported by the patient or reported in response to the open question from the study personnel: ‘Have you had any health problems since the previous visit/you were last asked?’, or revealed by observation will be collected and recorded in the CRF. When collecting AEs, the recording of diagnoses is preferred (when possible) to recording a list of signs and symptoms. However, if a diagnosis is known and there are other signs or symptoms that are not generally part of the diagnosis, the diagnosis and each sign or symptom will be recorded separately.

Adverse Events based on examinations and tests

The results from CSP-mandated laboratory tests and vital signs will be summarised in the CSR. Deterioration as compared to baseline in CSP-mandated laboratory values, vital signs, or ECGs should therefore only be reported as AEs if they fulfil any of the SAE criteria or are the reason for discontinuation of treatment with the IP.

If deterioration in a laboratory value/vital sign/ECG is associated with clinical signs and symptoms, the sign or symptom will be reported as an AE and the associated laboratory result/vital sign/ECG will be considered as additional information. Wherever possible, the reporting Investigator uses the clinical, rather than the laboratory term (eg, anaemia versus low haemoglobin value). In the absence of clinical signs or symptoms, clinically relevant deteriorations in nonmandated parameters should be reported as AE(s).

Any new or aggravated clinically relevant abnormal medical finding at a physical examination as compared with the baseline assessment will be reported as an AE.

NB. Cases where a patient shows an AST **or** ALT ≥ 3 times the ULN **or** total bilirubin ≥ 2 times the ULN may need to be reported as SAEs, please refer to [Appendix D](#) ‘Actions required in cases of combined increase of Aminotransferase and Total Bilirubin – Hy’s Law’, for further instructions.

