3. IDENTIFICATION OF POTENTIAL HY'S LAW CASES

In order to identify cases of PHL it is important to perform a comprehensive review of laboratory data for any patient who meets any of the following identification criteria in isolation or in combination:

- ALT $\geq 3xULN$
- AST $\geq 3xULN$
- TBL $\geq 2xULN$

When a patient meets any of the identification criteria, in isolation or in combination, the central laboratory will immediately send an alert to the Investigator (also sent to AstraZeneca representative).

The Investigator will also remain vigilant for any local laboratory reports where the identification criteria are met, where this is the case the Investigator will:

- Request a repeat of the test (new blood draw) by the central laboratory
- Complete the appropriate unscheduled laboratory CRF module(s) with the original local laboratory test result

When the identification criteria are met from central or local laboratory results the Investigator will without delay:

- Determine whether the patient meets PHL criteria (see Section 2 of this Appendix for definition) by reviewing laboratory reports from all previous visits (including both central and local laboratory results)

The Investigator will without delay review each new laboratory report and if the identification criteria are met will:

- Notify the AstraZeneca representative
- Determine whether the patient meets PHL criteria (see Section 2 of this Appendix for definition) by reviewing laboratory reports from all previous visits
- Promptly enter the laboratory data into the laboratory CRF

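### Section 5.8: the 3 to 5x ULN liver rule is triggered by either enzyme, but its mandatory stop is worded as needing both to rise, so a single rising enzyme has no literal stop

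*Protocol*

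**What the plan says.** The rule is in Section 5.8 of the protocol, after the list of absolute liver stops. It has four parts.

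- **Trigger:** "If an increase in ALT or AST more than 3 times ULN but less than 5 times ULN with normal total bilirubin level", together with absence of signs or symptoms of hepatic injury. The result must be confirmed by an immediate repeat.
- **Mandatory stop:** "If the repeat ALT and AST are trending up", the patient must leave the study.
- **Monitoring permission:** "if the repeat ALT and AST levels are trending down, the elevations may be monitored for up to 14 days from the initial finding", at a frequency of 2 to 3 tests a week.
- **Time limit:** "If the levels have not normalised by the fourteenth day after the initial finding, the patient must be discontinued from the study".

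The trigger joins the enzymes with *or*; both branches after the repeat join them with *and*. Elsewhere in the section the liver criteria use *or*: the three absolute stops, this trigger and the referral to Appendix D. Amendment 4 does not list Section 5.8 among the sections it changes, so this is current text.

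**The concern.** A stopping rule should give an instruction for the patient it is written for. This one is set off by a single raised enzyme, yet taken word for word its stop needs both enzymes to rise. The case left out is the one the rule exists to catch: the raised enzyme keeps climbing below 5 times ULN while the other does not follow it.

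Section 1.4 names a nonclinical potential for hepatotoxicity and relies on liver monitoring during the trial. Two sites could follow the same sentence and act differently on the same result, one stopping the patient and the other treating it as a matter of judgement. Section 5.8.1 also builds the study-level stopping rule on events that meet individual stopping criteria, so uncertainty about an individual criterion carries into that rule. Sample size, power and the primary analysis are not involved.

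**Working it through.** No figure in the plan needs reproducing. The check is to apply the text to the case in question and then see whether another provision supplies the missing instruction.

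**1. The branches, with the elevated enzyme rising.** Assume it stays between 3 and 5 times ULN, bilirubin is normal and there are no symptoms. The other enzyme can move in three ways.

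| Other enzyme on repeat | Stop (both up) | Monitoring (both down) | Literal result |
|---|---|---|---|
| Rising | met | not met | stop |
| Flat | not met | not met | no instruction |
| Falling | not met | not met | no instruction |

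The literal stop covers 1 of these 3 patterns. This counts patterns and is not a probability.

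**2. Other provisions, for ALT rising from 3.5 to 4.5 times ULN with AST flat.**

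- *Above 5 times ULN (Section 5.8):* 4.5 < 5, so not met.
- *Above 3 times ULN with symptoms or drug allergy, or with bilirubin above 2 times ULN (Section 5.8):* excluded by the assumptions of the rule.
- *Stop for an adverse event (Section 5.8):* "The patient has a clinically significant or serious AE that would not be consistent with continuation in the study" is available to the Investigator, the sponsor or the patient, but it is a judgement. Under Section 6.3.3, symptom-free deteriorations in mandated laboratory values "should therefore only be reported as AEs if they fulfil any of the SAE criteria or are the reason for discontinuation of treatment", so here the adverse event route largely presupposes the decision to stop.
- *Appendix D:* a value of at least 3 times ULN alerts the Investigator and the sponsor. With normal bilirubin the potential Hy's Law criteria are not met, and the instruction becomes: "Perform follow-up on subsequent laboratory results according to the guidance provided in the Clinical Study Protocol". That leads back to the text with the gap.
- *Section 6.3.5:* repeat testing and follow-up at the Investigator's judgement, with no stop.
- *Scheduled chemistry (Tables 1 and 2):* Days 7, 14, 21 and 28, each ±1 day, and follow-up. The nominal interval is 7 days and the longest is 7 + 1 + 1 = 9 days, against 2 to 3 tests a week in the monitoring branch.

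**3. What the 14-day limit can do.** The last dose is on the morning of Day 28. For an elevation detected at a scheduled visit, the nominal dosing time left is:

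- Day 7: 28 − 7 = 21 days
- Day 14: 28 − 14 = 14 days
- Day 21: 28 − 21 = 7 days
- Day 28: 0 days

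Even read as covering every triggered case, the limit shortens dosing only after a Day 7 elevation, by 21 − 14 = 7 days. It does not replace a stop at the repeat test.

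**4. Number exposed.** Three active groups of 14 give 3 × 14 = 42 of the 56 planned patients. The protocol gives no rate for the trigger, so no expected number of cases can be calculated.

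**The case against.** The best defence is that this is clinical prose and not Boolean logic. Both enzymes are in the standard chemistry panel, so naming both may simply identify the repeated results, and the reference to monitoring the elevations points to whichever enzyme triggered the rule. Monitoring is also a permission, introduced as the exception to stopping, so a cautious site would not take silence as leave to continue. The patient is re-tested about weekly in any case, the sponsor is alerted, dosing lasts only 28 days, and the protocol reports no clinical hepatotoxicity to date. All of this stands, and it keeps the point small. It does not make the sentence say what it should: the loose reading is likely but not stated, and the safeguards consist of alerts, judgement and higher thresholds.

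Three stronger readings are tempting, and the documents do not support them.

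- *Most repeat results are unassigned.* Crossing up, flat and down for both enzymes gives 3 × 3 = 9 patterns, of which only both up and both down are assigned, leaving 7. That count gives a normal, untriggered enzyme the same weight as the elevated one. It also includes patterns with no rise; flat in both would stay unassigned even if both branches said *or*.
- *The patient is left unmonitored.* The scheduled chemistry and the alert show otherwise.
- *Flat values must also force a stop.* Nothing in the protocol implies this. It would be a new stopping policy and not a correction of the wording.

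**Conclusion.** The point holds as a minor wording defect in a safety rule: wrong as written, and worth correcting. Followed literally, Section 5.8 sets no mandatory stop for a patient whose elevated enzyme keeps rising between 3 and 5 times ULN while the other is flat or falling, and no other section supplies one. The conclusion rests on the literal reading, normal bilirubin and no symptoms. Few patients would be affected out of at most 42 planned on active drug, many Investigators would stop such a patient anyway, and an unnoticed case is unlikely. No efficacy or safety analysis changes.

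**What to change.** Replace the two branches in Section 5.8 with wording to this effect:

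> If, on repeat, ALT or AST (whichever is above 3 times ULN) is rising, the patient must be discontinued. If every enzyme above 3 times ULN is falling, monitoring 2 to 3 times per week is allowed for no more than 14 days after the elevation was detected.

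State that an enzyme counts as above 3 times ULN if it was so at either the first or the repeat test. Keep the 14-day sentence and say that it applies to every triggered case. The sponsor should decide how to handle a flat repeat value; no automatic stop is needed for flat values or for changes within the normal range.

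This restores the *or* used in the section's other liver criteria and resolves both open rows of the table to a stop. The cost is a short edit to one paragraph, made through a protocol amendment. The downside is that a few patients with a rise in one elevated enzyme only would be stopped who might otherwise have continued.
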